9.4.4.1 Safety Monitoring

Following ICV access device placement, subjects and their caregivers will be given written instructions providing details on signs and symptoms of concern for device complications and instruction on when to return to the site for device evaluation. Patients will be admitted to the hospital for every BMN 190 infusion. For all infusions, subjects will be monitored in an appropriate inpatient setting for a minimum of 24 hours from the start of the infusion. For the first infusion only, subjects will also return for a follow-up visit to clinic 72 hours (and no later than the third calendar day) after the start of infusion. After all visits, the parent or legal guardian will be telephoned within 48 hours to determine health status.

Vital signs (Section 9.7.5.1) will be measured within 30 (\pm 5) minutes before infusion start or restart, every 30 (\pm 5) minutes during infusion, 0.5 hours (\pm 5 minutes), 1 hour (\pm 5 minutes), and 4 hours (\pm 15 minutes) after infusion end, and then every 4 hours (\pm 15 minutes) for the next 16 hours. Blood pressure will be measured in the upper arm using an appropriately sized blood pressure cuff. If the patient's blood pressure is abnormal (as compared to site-specific reference ranges), a manual blood pressure will be obtained by a trained healthcare professional.

For the first infusion of BMN 190, continuous ECG monitoring (3- or 5-lead) will be performed for all subjects. The ECG should begin 15 (\pm 5 minutes) prior to infusion start, continue through infusion of BMN 190, and end after infusion of flushing solution. In the event that the subject has already received the first infusion of BMN 190, the next infusion will be monitored as above. If a 12-lead ECG is required during this time, continuous monitoring should be interrupted in order to obtain the 12-lead ECG.

A standard ECG (12-lead), including heart rate, rhythm, intervals, axis, conduction defects, and anatomic abnormalities, will be performed 30 (\pm 5) minutes after infusion end at the first infusion and every 24 weeks thereafter. In patients with present or past bradycardia,

conduction disorders, or with structural heart disease, an ECG will be performed within 30 minutes before the start of infusion (± 5 minutes), at 2 hours (± 15 minutes) during infusion, 30 (± 5) minutes after infusion end, and 12 hours (± 3 hours) after infusion end for each study drug infusion.

Subjects require regular monitoring for adverse events and epileptic seizures by appropriately trained personnel throughout the duration of the infusion. If epileptic seizures develop, the infusion may be interrupted at the discretion of the investigator. Because hypersensitivity reactions (anaphylaxis or general allergic) may occur, it is required that appropriately trained personnel and equipment for emergency resuscitation (including epinephrine) be available near the bedside during study drug infusion. In case emergency treatment is needed, all subjects should have an intravenous line during infusion. If the prior 3 study drug infusions were completed without significant adverse events, an intravenous access line does not have to be placed prior to infusion as consistent with local hospital policies. However, supplies for placing emergency access and all emergency medication must be readily available should they be needed. For information regarding the reporting of hypersensitivity reactions, refer to Section 10.4.1.

Symptoms of hypersensitivity reactions may include fever, chills/rigors, skin symptoms (urticaria, angioedema, rash), respiratory symptoms (dyspnea, wheezing, stridor), gastrointestinal symptoms (nausea, vomiting, abdominal pain), and/or cardiovascular changes (hypotension/hypertension). If more severe symptoms, such as angioedema (tongue or throat swelling) or stridor, develop, the infusion should be stopped.

To date there has been no anaphylaxis or anaphylactoid reactions in studies with BMN 190. However, in the event of a suspected anaphylactic reaction, serious hypersensitivity event, or severe hypersensitivity (defined as a hypersensitivity event of Grade 3 or higher), blood samples to assess C4, serum tryptase, and total IgE will be collected within 1 hour of the event and tested; a blood sample to assess drug-specific IgE will be collected no sooner than 8 hours after the event (or before the next infusion).

Safety assessments will be conducted during and after each infusion. Subjects may be required to stay for a longer observation period at the investigator's discretion. If an AE consistent with a hypersensitivity reaction (Section 7.4.1) is observed, appropriate intervention may include infusion interruption, infusion rate decrease, or administration of antihistamine, oxygen, fluids, or steroids. If infusion is restarted after interruption, the initial rate should be approximately one-half the rate at which the reaction occurred. Further detail for infusion modification is provided in the Study Pharmacy Manual.

BOMARIN

The parent or legal guardian will be instructed to contact the investigator to discuss any AE subsequent to discharge.

The use of ICV access devices can result in infections, intracerebral hemorrhage from chronic reservoir use, reservoir leakage, and seizures (Karavelis, 1996) (Kronenberg, 1998). Additional surgery may be required to fix or replace the devices. Patients will be monitored throughout the study for potential infections (high temperature, cough, rash, headache, swelling or drainage in the incision area) and signs of ICV reservoir leakage or failure (refer to the Study Pharmacy Manual).

Because of the inherent safety considerations surrounding the implanted device, arrangements should be made for the subject to have the ICV access device removed no more than 4 weeks after either the Study Completion visit or the Early Termination visit. All removed or replaced implantable ICV devices must be returned to BioMarin in order to evaluate the material integrity of the reservoir, and all other devices (as described in the Pharmacy Manual) except for infusion pumps, should also be returned. If the subject intends to continue to receive BMN 190 following participation in this study (e.g., via commercial product, use in a registry, or another BMN 190 study), then the device does not need to be removed. Following device removal, subjects should return to the site 4 weeks (±3 days) later for a safety follow-up visit.

9.4.5 Method of Assigning Subjects to Treatment Groups

Subjects will be enrolled as they become available and without attention to any entry criterion or other patient characteristic.

9.4.6 Selection of Dose

BMN 190 will be administered by ICV infusion every 14 days (\pm 3 days) according to the patient's age:

- birth to < 6 months: 100 mg
- 6 months to < 1 year: 150 mg
- 1 year to < 2 years: 200 mg (first 4 doses), 300 mg (subsequent doses)
- ≥ 2 years: 300 mg

Patients younger than 2 years will start the study at the dose level appropriate for their age and will transition to the dose level consistent with their age as they mature.

The 300 mg dose level was derived from dose levels used in the TPP1-null dachshund study (Vuillemenot, 2011). Pharmacological effects, including functional improvement and life extension, have been robustly demonstrated in TPP1-null dachshunds at 4 mg and Proprietary and Confidential 05 February 2019

BIOMARIN 190-203 Amendment 6

16 mg dose levels. Since TPP1 activity in brain tissue is proximally related to CNS lysosomal storage materials, scaling by brain mass is judged to be predictive of the human therapeutic dose. Human-equivalent doses were calculated by brain mass scaling. The human brain on average achieves about 75% of adult mass by age 2 and 100% by age 5 (Giedd, 1996). If adult human brain mass is 1400 g, the range for healthy children aged 2 to 7 years would be 1050 to 1400 g. Given progressive brain atrophy in CLN2 disease patients, an average mass of 1000 g was assumed, producing a scaling factor of 20-fold based on average dachshund brain mass of 50 g.

The no-observed-adverse-effect level (NOAEL) which also yielded clinical disease benefit from nonclinical studies in Dachshund was 48 mg, which would correspond to 960 mg in human.

BMN 190 dose scaling by brain mass has been used to target similar drug concentrations in CNS tissue and scaled doses have yielded similar PK in CSF when applied across species (i.e., dog, monkey and human). This approach supports a dose of 300 mg every 14 days down to 1 year of age, where the human brain has reached approximately 68-73% of its adult mass, or 0.94 kg and 0.97 kg for females and males, respectively (Dekaban, 1978). Subjects less than 1 year of age will receive a reduced dose, scaled by brain mass, and will escalate to the next dose level as they age on the study. As an additional precaution, subjects aged between 1 to < 2 years will receive an initial dose of 200 mg for the first 4 doses to assess the safety, tolerability and PK of BMN 190 before being escalated to the 300 mg dose level. This dosing plan enables enrollment of subjects who are younger than 2 years of age.

The age-specific dose of BMN 190 will be infused at a uniform rate of 2.5 mL/hour for all subjects, thus requiring shorter total infusion times for subjects administered doses lower than 300 mg. The total infusion volume and infusion rate is within the physiologic functional range in relation to the brain volume, CSF volume and CSF turnover rate of children < 3 years of age. The total volume of CSF in an infant is approximately 50 mL, thus the total volume of BMN 190 infused (3.3 mL) is less than 10% of this volume. Furthermore, since at least 2 mL of CSF will be collected prior to each infusion for surveillance laboratory testing, the total drug volume infused is not expected to be of physiologic consequence as it pertains to changes in intracerebral pressure.

CSF production rates in humans have been calculated to be 0.3–0.4 ml/min, which translates to an hourly production rate of approximately 20 ml (Pappenheimer, 1962). A more recent retrospective study of 100 children (61 males, 39 females; age 0.02 to 15.7 years) with hydrocephalus due to various causes measured hourly CSF production output as reflected by the output through an external ventricular drainage (EVD) (Yasuda, 2002). The mean (SD)

BIOMARIN 190-203 Amendment 6

hourly rate of CSF output was 8.1 (5.2) mL/h. A regression analysis indicated that the age and body weight appeared to correlate with the hourly CSF output. The regression equation is as follows: hourly CSF output = 2.78 - 2.23(male = 0, female = 1) + 0.97 log (age in years) + 2.26 log (body weight in kg). Thus, the predicted hourly CSF output even for a 6 month old child be approximately 2.5 to 4.7 mL, which exceeds the hourly rate of BMN-190 infusion of 2.5 mL, suggesting that the infusion rate is compatible with CSF physiology.

Lastly, this dosing strategy also has the added benefits of shortening the total infusion time for infants (approximately 1.3 to 1.5 hours) and toddlers (approximately 2.7 hours) and decreasing the possibility of dosing errors (since the smaller volume will be administered at a consistent rate).

The PK of BMN 190 will be assessed in this study to further confirm the appropriateness of this approach. In children younger than 2 years, dosing may be adjusted based on PK as described in Section 9.4.1.

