9 INVESTIGATIONAL PLAN

9.1 Overall Study Design and Plan

This will be a Phase 2 open-label, multicenter study in pediatric patients < 18 years of age with CLN2 disease, confirmed by deficiency of TPP1 enzyme activity and mutation of the CLN2 gene. The study is designed to assess disease progression in CLN2 patients treated with BMN 190 compared to natural history data from untreated historical controls (data from a CLN2 disease patient registry and data from siblings with CLN2 disease, when available). The comparison of treatment with untreated controls will be compared from the time of the initiation of study drug. A summary of events is provided by visit in Table 9.1.1

The planned enrollment for this study is at least 10 patients: at least 5 patients with a Hamburg ML score \geq 5 points, at least 5 patients with a ML score < 5 points, and at least 5 patients < 2 years of age. Study eligibility will be determined and enrollment will occur before (\leq 21 days) subjects are admitted to the hospital for surgical implantation of an ICV access device. The Baseline visit to collect clinical scores and clinical laboratory parameters will be completed no more than 2 days before the first infusion.

BMN 190 will be administered every 14 days from the date of the first infusion (\pm 3 days) for at least 144 weeks according to the patient's age:

- birth to < 6 months: 100 mg
- 6 months to < 1 year: 150 mg
- 1 year to < 2 years: 200 mg (first 4 doses), 300 mg (subsequent doses)
- ≥ 2 years: 300 mg

Patients younger than 2 years will start the study at the dose level appropriate for their age and will transition to the dose level consistent with their age as they mature. Upon study completion or early termination, all patients will be given the opportunity to participate in a postmarketing registry that will assess the long-term safety and efficacy of BMN 190 for patients receiving commercial drug.

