- ⁱ Device and surgical location of the device should be observed prior to each infusion for any swelling or signs of infection of the scalp or surrounding area.
- ^j Because hypersensitivity reactions may be associated with ERT administration, subjects should be pretreated with age-appropriate doses of antihistamine (and antipyretic, if appropriate) medication approximately 30 minutes (± 15 minutes) before BMN 190 infusions.
- ^k Subjects will be monitored in a nursing-intensive setting for a minimum of 48 hours post-ICV device placement and after the start of the first drug infusion. Following ICV access device placement, subjects and their caregivers will be given written instructions providing details on signs and symptoms of concern for device complications and instruction on when to return to the site for device evaluation. An additional follow-up telephone call will be conducted within 48 hours after inpatient discharge for all visits.
- ¹ Samples of CSF and plasma for PK analysis will be collected within 15 minutes before infusion start, and 0.25, 4, 8, 20 (±5 minutes), 72, and 120 (±15 minutes) hours after infusion end. Samples will be collected on Day 1, and Weeks 25, 49, and 97. There will be no PK samples collected at Week 73 or after Week 97.
- ^m Samples of blood and CSF will be collected prior to infusion. Collection of CSF will be every 2 weeks from Weeks 1 to 71 and every 8 weeks from Weeks 79 to 145; blood will be collected every 8 weeks from Weeks 1 to 49 and every 12 weeks from Weeks 61 to 145.
- ⁿ Samples of blood (serum) and CSF will be collected for TAb and NAb testing before the first infusion (Baseline or Week 1 before the infusion), every 12 weeks thereafter, and at the Study Completion Visit. Samples of blood (serum) will be collected for TAb testing at the Device Safety Follow-Up and Safety Follow-Up visits (or within 1 week of the Early Termination visit). Collection must precede infusion. NAb will be tested at baseline and at subsequent time points when TAb is positive. Samples of blood (serum) will be collected to assess baseline total and drug-specific IgE levels in the event of later hypersensitivity reactions requiring additional lab work (as outlined in note x below).

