Dosing can be adjusted in the judgement of the investigator, upon consultation with the medical monitor, to manage AEs as outlined above. Should the dose-limiting AE resolve in

BIOMARIN 190-203 Amendment 6

the opinion of the investigator, and upon consultation with the medical monitor, dosing at the full dose may resume.

In patients younger than 2 years, dosing may also be adjusted by the sponsor in consultation with the investigator and medical monitor based on results from PK analysis, as follows:

- Within a patient, if the observed CSF AUC_{0-t} exceed the range of CSF AUC_{0-t} characterized with the 300 mg dose in Study 190-201, the dose may be reduced to 50% of the recommended age-appropriate dose.
- Within a patient, if the observed CSF AUC_{0-t} is less than the range of CSF AUC_{0-t} characterized with the 300 mg dose in Study 190-201, the dose may be increased to the recommended dose for the next oldest age group.

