9.7.4 Pharmacokinetics Variables

On Day 1 and Weeks 25, 49, and 97 samples of CSF and plasma for serial PK will be collected within 15 minutes before infusion start, and 0.25, 4, 8, 20 (\pm 5 minutes), 72, and 120 (\pm 15 minutes) hours after infusion completion. The following parameters will be evaluated by non-compartmental analysis:

- Area under concentration-time curve from time 0 to infinity $(AUC_{0-\infty})$
- Area under concentration-time curve from 0 to the time of last measurable concentration (AUC_{0-t})
- Maximum observed concentration (C_{max})
- Time to reach $C_{max}(T_{max})$
- Elimination half-life $(t_{\frac{1}{2}})$
- Apparent clearance of drug (CL/F)
- Apparent volume of distribution based on terminal phase (Vz/F)

If a subject discontinues the study within 48 hours after an infusion completion, plasma and CSF samples should be drawn during the Early Termination visit.

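### The four 200 mg doses are said to assess PK before the step to 300 mg, but the fixed PK weeks do not guarantee a 200 mg profile in infants who turn 1 on study

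*Protocol*

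**What the plan says.** Protocol 9.4.6 describes the 200 mg period as an added precaution for children aged 1 to under 2 years: an "initial dose of 200 mg for the first 4 doses to assess the safety, tolerability and PK of BMN 190 before being escalated" to 300 mg. The same section says "Patients younger than 2 years will start the study at the dose level appropriate for their age" and then move up through the levels as they get older, so a child who enters under 1 year reaches 200 mg during the study.

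PK sampling runs by study week. Table 9.1.1, footnote l: "Samples will be collected on Day 1, and Weeks 25, 49, and 97", and "There will be no PK samples collected at Week 73 or after Week 97". Section 9.7.4 gives the same four occasions, 12.8 repeats the three later weeks, and the PK windows in SAP Appendix 1 are also defined by study week. The only other scheduled PK draw is at Study Completion or Early Termination (Table 9.1.1, 12.10), too late to inform the step to 300 mg in a child who stays on study. No section triggers PK sampling when the dose level changes.

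For children under 2 years, Protocol 9.4.1 adds that "dosing may also be adjusted by the sponsor in consultation with the investigator and medical monitor based on results from PK analysis", using the child's own CSF AUC against the range seen at 300 mg in Study 190-201.

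**The concern.** The protocol gives the 200 mg doses a purpose that the sampling schedule secures only for some of the children who receive them. A child who ages into the 1-year group starts 200 mg at whatever study week the first birthday falls in, and the four doses occupy only four consecutive fortnightly visits. A profile at Week 25 or Week 49 lands on one of them only by coincidence.

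What is at stake is a written precaution for the youngest patients. An infant could go to 300 mg without any exposure measurement at 200 mg, and the AUC comparison in 9.4.1 would then have nothing to work with at that level. The study's PK data at 200 mg would also come mainly from children first dosed after their first birthday.

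**Working it through.** The documents give no figure for PK coverage at 200 mg, so there is none to reproduce. The schedule can be enumerated.

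**Inputs**
- Infusions every 14 days from the first (Protocol 9.1): dose k is given 14k days after the first infusion, in Week 1 + 2k.
- PK at Day 1 and Weeks 25, 49 and 97 (footnote l, 9.7.4): k = 0, 12, 24 and 48.
- Levels by age (Table 9.4.1.1): 100 mg under 6 months, 150 mg from 6 months to under 1 year, then 200 mg for four doses, then 300 mg.
- Assumption: a month is 365.25/12 = 30.4375 days.
- Assumption: where a single percentage is given, age at first infusion is uniform over 0-12 months. The documents give no age distribution under 1 year. They require at least 5 patients under 2 years and set no number under 1 year.

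**Reading A: the four doses are counted from the first birthday**

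Let T be the days from first infusion to first birthday. The first 200 mg dose is k* = T/14 rounded up, and the 200 mg doses are k* to k* + 3. A profile falls on one of them only if that run contains 12 or 24, so k* must be 9-12 or 21-24. The first 200 mg dose is then at Week 19, 21, 23 or 25, or at Week 43, 45, 47 or 49.

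- By visit: 8 of 26 possible starting visits are covered; 18/26 = 69.2% are not.
- By day: covered when 112 < T ≤ 168 or 280 < T ≤ 336, which is 112 of 365.25 days. Uncovered share = 1 − 112/365.25 = 69.3%.
- By entry age, a = (365.25 − T)/30.4375: T = 336 and 280 give 0.96 and 2.80 months; T = 168 and 112 give 6.48 and 8.32 months.
- With the ±3-day visit window simulated: 69.1%.
- With the youngest age at first dose at about 2 or 7 weeks: 68-71%.

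The answer depends heavily on entry age:

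| Entry age, uniform within (months) | No 200 mg profile |
|---|---|
| 0-3 | 39% |
| 3-6 | 100% |
| 6-9 | 39% |
| 9-12 | 100% |
| 6.5-8.3 | 0% |

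Example: a child who enters at 3 months has 200 mg doses at Weeks 41, 43, 45 and 47. The four profiles are at 100, 150, 300 and 300 mg, and Week 49 misses the 200 mg doses by one visit.

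**Reading B: the four doses are the first four on study**

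These are at Weeks 1, 3, 5 and 7. A child who enters under 1 year receives 200 mg only if the birthday falls within 42 days of the first infusion: 42/365.25 = 11.5% under uniform entry. The Day 1 profile precedes the birthday and Week 25 comes after the fourth dose, so none of these children has PK at 200 mg.

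**The other levels**
- 100 mg: always profiled, on Day 1.
- 150 mg, entry at 6-12 months: profiled on Day 1.
- 150 mg, entry under 6 months: Week 25 is 168 days after the first dose, so it falls at 150 mg once entry age is at least (182.625 − 168)/30.4375 = 0.48 months. For younger entry, Week 49 (336 days) does.
- 300 mg: Week 97 is 672 days after the first dose, when every child is past the 200 mg doses.

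So only the 200-to-300 mg step can lack data from the level being left.

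**The case against.** The strongest case on the other side is that little depends on this. Children who enter at 1 to under 2 years have their Day 1 profile at 200 mg with three more 200 mg doses to follow, so for them the precaution works as described. The 200 mg doses also serve safety and tolerability, which are watched at every infusion by at least 24 hours of inpatient monitoring, vital signs and CSF surveillance, with quarterly review by the Data Review Board in the first year. The adjustment text in 9.4.1 is permissive, and nothing requires a profile at every level in every child. The aim stated at the end of 9.4.6 is to confirm the dosing approach in the study as a whole. The children affected may be few, or none.

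All of that stands, and it limits the point. It does not remove it: 9.4.6 names PK as something assessed before escalation, and no section secures this for children who age into the group.

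A reader might go further and infer that most infants step up at each level without exposure data, or that PK-based adjustment cannot work in infants. The documents do not support this. The 100 and 150 mg levels are always profiled before they are left, 300 mg is always profiled later, and 9.4.1 can be applied to any AUC that is observed. Nor is 69% a property of the plan. It follows from an assumed age distribution and one of two readings of the four-dose count.

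**Conclusion.** The point holds in limited form. For children who enter under 1 year and turn 1 on study, the protocol does not guarantee the 200 mg PK that 9.4.6 gives as a purpose of those doses. Counted from the first birthday, a 200 mg profile is obtained only for entry at about 1.0-2.8 or 6.5-8.3 months. About 69% would miss it under uniform entry over 0-12 months, with a possible range of 0-100% among an unstated number of infants. Counted from the start of the study, none would have it. Children who enter at 1 to under 2 years are not affected, and neither are the 100 and 150 mg levels. This is a mismatch between a stated purpose and a sampling schedule. It is not evidence that any dose is unsuitable.

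**What to change.** Reconcile Protocol 9.4.6, and the PK-based adjustment text in 9.4.1, with footnote l of Table 9.1.1, 9.7.4 and 12.8. State how the four doses are counted for a child who ages into the 1-year group. In the same pass, reconcile SAP 4.2, which places 300 mg after the second birthday, with the protocol's schedule.

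Then do one of the following.

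1. For children who turn 1 on study, move one existing PK occasion, Week 25 or Week 49, into the 200 mg doses, choosing the one that leaves a profile at every level received. Keep Day 1 and Week 97. With the doses counted from the first birthday, enumeration shows this is possible for every entry age under 12 months and adds no draws. For entry at 3 months, for example, the Week 49 profile would move to Week 47. The cost is that one fixed-week profile shifts for these few children. Under uniform entry, and taking the nearest suitable dose, the mean shift is about 6 weeks when children already covered count as zero. The largest is about 30 weeks, for entry close to birth, where Week 25 would move to Week 55. The PK windows in SAP Appendix 1 need a matching rule for these children.
2. If the fixed weeks are kept, limit the statement that the 200 mg doses assess PK to children who enter at 1 to under 2 years. This costs only a text change.

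Neither option changes a dose or a dose-adjustment rule.

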9.4.1 Treatments Administered

BMN 190 will be administered by ICV infusion every 14 days (\pm 3 days), preferably in the morning, according to the patient's age:

- birth to < 6 months: 100 mg
- 6 months to < 1 year: 150 mg
- 1 year to < 2 years: 200 mg (first 4 doses), 300 mg (subsequent doses)
- ≥ 2 years: 300 mg

BIOMARIN 190-2

190-203 Amendment 6

Patients younger than 2 years will start the study at the dose level appropriate for their age and will transition to the dose level consistent with their age as they mature.

Fasting for a minimum of 2 hours may be considered for the first infusion and subsequent infusions until the subject's reaction to the study drug is determined. When a feeding tube is used, the tube may be turned off 2 hours before infusion.

The normal infusion will be administered over 4 (± 1) hours at a rate of 2.5 mL/hr; the dose will be determined by the patient's age. Subjects not receiving the full 300 mg dose (administered in a total volume of 10 mL), will receive the appropriate volume at a rate of 2.5 mL/hr for over a shorter duration of time (see Table 9.4.1.1 below).

Age	Dose	Rate	Infusion Time	Dose Modification Options (AEs)
birth to < 6 months	100 mg	2.5 mL/hr	1.3 hours (±0.5 hr)	 Reduce infusion rate and administer drug over 2 hours Reduce the dose by 50% administered over the 1.3 (±0.5) hours Reduce the infusion rate and administer 50% of the target dose over 2 hours
6 months to < 1 year	150 mg	2.5 mL/hr	2 hours (±0.5 hr)	 Reduce infusion rate and administer drug over 3 hours Reduce the dose by 50% administered over the 2 (± 0.5) hours Reduce the infusion rate and administer 50% of the target dose over 3 hours
1 year to < 2 years	200 mg (first 4 doses),	2.5 mL/hr	2.7 hours (±1 hr)	• Reduce infusion rate and administer drug over 4 hours (200 mg); 6 hours (300 mg)
	300 mg (subsequent doses)	2.5 mL/hr	4 hours (±1 hr)	 Reduce the dose by 50% administered over the 2.7 (±1) hours (200 mg); 4 (±1) hours (300 mg) Reduce the infusion rate and administer 50% of the target dose over 4 hours (200 mg); 6 hours (300 mg)
≥2 years	300 mg	2.5 mL/hr	4 hours (±1 hr)	 Reduce infusion rate and administer drug over 6 hours Reduce the dose by 50% administered over the standard time of 4 (± 1) hours Reduce the infusion rate and administer 50% of the target dose over 6 hours

 Table 9.4.1.1: Age-Specific Dosing Schema for BMN 190 Administration

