9.4.6.2 Selection of Infusion Volume and Rate

The nonclinical studies in the dachshund and cynomolgus monkey utilized an infusion rate of approximately 5% of the total CSF volume per hour. This was expected to represent a safe infusion rate that would minimize changes in total CSF volume and intracranial pressure. The dachshunds received ICV infusions at a rate of 0.6 mL/hour for 2-4 hours, while monkeys received 0.88 mL/hour for 3.6 hours. No effects were observed in these studies indicative of safety concerns due to the infusion rate. In the CLN2 patient population, the estimated CSF volume is approximately 100 mL. For the proposed clinical trial, a volume of 10 mL infused over a 4 hour period represents an infusion rate of 2.5% of the total CSF volume per hour, which is approximately half the rate that had no safety effects in the nonclinical studies.

Therefore, we expect that 10 mL infused over 4 hours would be safe in CLN2 patients. This infusion rate has been used, with acceptable results, in the 48-week, Phase 1 / 2, 190-201 clinical trial (completed) and ongoing 190-202 extension study.

In subjects less than 2 years of age, the infusion volume will be reduced in accordance with their age-specific dose (Section 9.4.1) to account for differences in brain mass and CSF volume in younger subjects.

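### The 12-lead ECG set for 2 hours into infusion in children with cardiac risk falls after a nominal 100 mg infusion has ended

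*Protocol*

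**What the plan says.** **Dose and rate.** Protocol Section 9.4.6 states: "The age-specific dose of BMN 190 will be infused at a uniform rate of 2.5 mL/hour for all subjects". Table 9.4.1.1 gives 2.5 mL/hr in its Rate column for every age band, with nominal infusion times of 1.3 h (100 mg), 2 h (150 mg), 2.7 h (200 mg) and 4 h (300 mg). The times carry a tolerance of ±0.5 h for the two lower doses and ±1 h for the two higher ones. The full 300 mg dose is given in 10 mL, and Section 9.4.6 puts the smallest dose at 3.3 mL.

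**ECG.** Children with present or past bradycardia, a conduction disorder or structural heart disease have four 12-lead ECGs around an infusion: within 30 (±5) minutes before the start; 2 hours (±15 minutes) in, described as during the infusion; 30 (±5) minutes after the end; and 12 (±3) hours after the end. Sections 9.1, 9.4.4.1 and 9.7.5.4 apply this to each study drug infusion. The schedule is repeated in Table 9.1.1 footnote e, Sections 12.3.2.1 and 12.4, and the double-asterisk footnote to SAP Appendix 1. None of these places adapts the 2-hour time to dose or age.

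**The concern.** Two hours is the midpoint of a 4-hour infusion. It suits the 300 mg dose but was not rescaled for the shorter infusions given to children under 1 year. If the infusion is over before the ECG is due, the recording meant to show cardiac effects while drug is running shows the post-infusion state instead and repeats the ECG scheduled next. The children affected are those whom the protocol singled out for closer cardiac monitoring. Cardiovascular events and ECG adverse events are also on its list of events of special interest (Section 10.1.3).

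**Working it through.** **Inputs.** Concentration: 300 mg / 10 mL = 30 mg/mL (Section 9.4.1). Rate: 2.5 mL/hr (Section 9.4.6 and Table 9.4.1.1). ECG timing: Table 9.1.1 footnote e. The 2 hours are counted from the start of infusion.

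**Formulas.** Volume = dose / 30. End of infusion = volume / 2.5. During-infusion ECG window = 2 h ± 0.25 h = 1.75 to 2.25 h. Post-infusion ECG = end + 25 to 35 minutes = end + 0.42 to 0.58 h.

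| Dose | Volume (mL) | End at 2.5 mL/hr (h) | Time in Table 9.4.1.1 (h) | Part of the 1.75–2.25 h window inside the infusion | Post-infusion ECG (h) |
|---|---|---|---|---|---|
| 100 mg | 3.33 | 1.33 | 1.3 | none | 1.75–1.92 |
| 150 mg | 5.00 | 2.00 | 2 | 1.75–2.00 (half) | 2.42–2.58 |
| 200 mg | 6.67 | 2.67 | 2.7 | all | 3.08–3.25 |
| 300 mg | 10.00 | 4.00 | 4 | all | 4.42–4.58 |

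The plan's nominal times reproduce, as does its 3.3 mL for the smallest dose.

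**100 mg.** The infusion ends at 1.33 h. The ECG window opens 1.75 − 1.33 = 0.42 h (25 minutes) later, and its target comes 2.00 − 1.33 = 0.67 h (40 minutes) later. The post-infusion ECG lies wholly inside the during-infusion window. The remaining two ECGs come before the start and about 12 hours after the end. None of the four falls between 0 and 1.33 h. Section 9.7.5.4 words the post-infusion ECG as within, rather than at, 30 minutes of the end. That could bring it forward but still places it after the infusion.

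**150 mg.** The infusion ends exactly at the ECG target. An ECG taken in the first half of its window is during infusion; one in the second half is not.

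**Slower infusions.** At the upper tolerance for 100 mg (1.3 + 0.5 = 1.8 h), the overlap with the ECG window is 1.75 to 1.80 h, or 3 minutes. If an adverse event leads to 100 mg being given over 2 hours, as the table allows, the ECG target coincides with the end.

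**Check of the remedy.** Mid-infusion is 1.33 / 2 = 0.67 h for 100 mg and 2.0 / 2 = 1.0 h for 150 mg. With ±15 minutes, the windows are 0.42 to 0.92 h and 0.75 to 1.25 h, both wholly inside the infusion.

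**The case against.** **The group is tiny and still watched.** The child must be under 1 year and have one of the listed cardiac conditions. Section 9.3.2 excludes contraindications to neurosurgery and names congenital heart disease as an example. The first infusion has continuous 3- or 5-lead monitoring, heart rate is taken every 30 minutes during every infusion, and the other three 12-lead ECGs remain. The documents do not show that any such child was treated. All of this stands, and it limits the size of the point. It does not make the 2-hour instruction workable at 100 mg, and bradycardia and conduction disorders are not named in the exclusion. The Study Pharmacy Manual is not among the documents, so it could contain a correction, but the protocol text would still be wrong in six places.

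**Stronger readings that the documents do not support.** A reader might infer from the symmetric time tolerance that Table 9.4.1.1 lets a full dose run fast: 3.33 / 0.8 = 4.2 mL/hr for 100 mg, and 5 / 1.5 = 3.3, 6.67 / 1.7 = 3.9 and 10 / 3 = 3.3 mL/hr for the others. It does not. The 2.5 mL/hr Rate column applies together with the time, so such an infusion would breach the protocol. Section 9.4.4 requires a syringe pump with rate accuracy, and every rate change listed in the table is a reduction. The short end of the window has a legitimate use: "Reduce the dose by 50% administered over the 1.3 (±0.5) hours" gives 1.67 mL, which even in 0.8 h is 2.1 mL/hr.

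A reader might also object that the safety margin disappears in infants. Section 9.4.6 says "The total volume of CSF in an infant is approximately 50 mL", so 2.5 mL/hr is 2.5 / 50 = 5% per hour, equal to the animal rate and not half of it. But the statement in Section 9.4.6.2 that 10 mL over 4 hours "represents an infusion rate of 2.5% of the total CSF volume per hour, which is approximately half the rate that had no safety effects" is tied to about 100 mL of CSF, and children under 2 years are treated separately there. A rate of 5% per hour was tested without safety effects, so it still supports 2.5 mL/hr. Extending the CSF-output regression below 6 months needs body weights and a log base that the protocol does not state. The approximate infant times in Section 9.4.6 are rationale, and the general 4-hour sentence in Section 9.1 follows text that already gives shorter times for lower doses.

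**Conclusion.** Wrong as written, and minor. At nominal timing the during-infusion 12-lead ECG cannot be taken during a 100 mg infusion and duplicates the post-infusion one. At 150 mg it is borderline, with half of its window after the end. At 200 mg and 300 mg it works at the prescribed rate. The conclusion assumes 30 mg/mL, an uninterrupted infusion at 2.5 mL/hr, and 2 hours counted from the start. This is a slip in safety scheduling: no dose, volume or nominal time is miscalculated, no harm is shown, and no efficacy analysis depends on it.

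**What to change.** For any dose whose planned infusion lasts 2 hours or less, set this ECG at mid-infusion (±15 minutes): about 0.7 h for 100 mg and 1.0 h for 150 mg. Keep 2 hours for longer infusions. Make the same change in Protocol Section 9.1, Table 9.1.1 footnote e, Sections 9.4.4.1, 9.7.5.4, 12.3.2.1 and 12.4, and the double-asterisk footnote to SAP Appendix 1.

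The cost is wording only. The number of ECGs is unchanged, and the SAP's 12-lead visit table has no separate row for a during-infusion recording, so no derived visit moves. A note in Table 9.4.1.1 that the rate governs the time would be an optional clarification.
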